Participants in the intervention (short duration) arm will receive antibiotics for up to 7 days. Antibiotics should be stopped from day 3 to 7 if respiratory cultures are negative and the patients fulfil a set of stringent clinical criteria signifying cardiopulmonary stability for 48 hours. If the respiratory cultures are positive, patients who fulfil the same set of clinical criteria should have their antibiotics stopped from day 5 to 7 (see section 8. Interventions). Antibiotics administered via all routes i.e. intravenous, oral and nebulisation should be stopped. Randomisation will be carried out when the participants fulfil the clinical stop criteria. The rationale for stopping antibiotics at the above time points is as follows:

Group 1: Short Duration arm

(a) Day 3

Patients who have negative respiratory cultures should have their antibiotics stopped from day 3 to 7 if the patient satisfies a set of criteria signifying clinical stability. As discussed above, though there are no randomised studies to support this, there are 2 observational studies [32, 33] showing that discontinuation of antibiotics in these cases did not result in a higher mortality or rate of new respiratory infections compared to those whose antibiotics were continued. In addition, those whose antibiotics were withheld had a lower rate of total secondary infections by MDROs. One of these studies concluded that antibiotics could be safely discontinued in patients with negative respiratory cultures with no significant impact on mortality, despite persistence of signs and symptoms of pneumonia in 35% of these patients [32]. The above studies have led to the recommendation in the 2016 IDSA/ATS guideline that for patients with suspected VAP whose respiratory invasive culture results are below the diagnostic threshold for VAP, antibiotics should be withheld rather than continued [3].

(b) Day 5-7

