7.7. Sample Handling

Respiratory cultures will be collected with the usual volume of 5-10ml per sample. Respiratory cultures may be collected via ETT, BAL or any other methods that the primary physician and local microbiology laboratories routinely use. Stool culture will be collected following defecation with the usual volume of 10-50g per sample. Stool samples are collected at recruitment, weekly during hospitalisation and day 28/60(± 5) after enrolment.

Microbiology cultures will be processed and reported in the local laboratories, which are expected to have standing quality control measures. Isolates, once identified, will be preserved, frozen and transported to an Oxford or Singapore study laboratory for genomic studies. These genomic results should concur with the initial microbiology laboratories' identification of the isolates.

a) Respiratory cultures

All samples will be cultured and identified via standard microbiological methods. Susceptibility studies will be performed using EUCAST or CLSI agar method and breakpoints. Culture results with antibiogram are usually available within 48 to 72 hours after sample collection.

Pathogens causing VAP and colonising MDROs will be processed for DNA extraction and undergo whole genome sequencing. These sequencing data will be used to track the spread of pathogens between hosts allowing for unobserved infection times, multiple independent introductions of the pathogen, and within-host genetic diversity.

These isolates will be de-identified and stored for up to 15 years for use in future ethically approved studies. We will seek permission from the participants to store their samples and include this in the informed consents.

b) Respiratory and stool samples

For microbiome analysis, respiratory and stool samples will be processed for DNA extraction. Shotgun metagenomics approach will be used to characterise microbial community dynamics in the respiratory and intestinal tract. The characteristics of the microbiota will be determined by comparing alpha and

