2. BACKGROUND INFORMATION

2.1. Objectives

Primary objective

To assess the effect of short (7 days or fewer depending on clinical response) versus long (8 days or more depending on physicians' preference) antibiotic treatment strategies on mortality and pneumonia recurrence within 60 days of enrolment in adults with ventilator-associated pneumonia (VAP) in Asia.

Secondary objectives

To compare the following endpoints according to treatment allocation within 60 days of enrolment:

- a) Ventilator-associated events
- b) Duration of mechanical ventilation
- c) Duration of hospitalisation
- d) Acquisition of multidrug resistant infection or colonisation during the hospitalisation
- e) Number of days of exposure to antibiotics during hospitalisation
- f) Number and types of extrapulmonary infections during hospitalisation (determined from cultures taken from sterile sites)
- g) Adverse events, i.e. antibiotic related diarrhoea, allergic reactions, readmissions

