2.3. Eligibility

Adult patients (≥ 18 years old) in participating wards who have been on mechanical ventilation for more than 48 hours who satisfy the following criteria are eligible for the study.

Inclusion Criteria

- a. Patients 18 years and older

- b. Invasive mechanical ventilation \geq 48 hours
- c. Satisfy the US Centers for Disease Control and Prevention National Healthcare Safety Network VAP diagnostic criteria ¹
 - o At least one of the following:
 1. temperature $> 38^{\circ}\text{C}$
 2. white blood cell count $\geq 12,000 \text{ cells/mm}^3$ or $\leq 4,000 \text{ cells/mm}^3$
 3. altered mental status with no other causes in > 70 year-olds; AND
 - o Two or more chest imaging tests demonstrating at least one of the following:
 1. new and progressive OR progressive and persistent infiltrate
 2. new and persistent OR progressive and persistent consolidation
 3. new and persistent OR progressive and persistent cavitation, AND
 - o At least two of the following:
 1. new onset of purulent sputum, or change in character of sputum, or increased respiratory secretions, or increased in suctioning requirements
 2. new onset or worsening tachypnea or dyspnea
 3. rales or bronchial breath sounds
 4. worsening gas exchange defined by oxygen desaturations (e.g., $\text{PaO}_2/\text{FiO}_2 < 240$), increased oxygen requirements or increased ventilation demand

Exclusion Criteria

- a. Poor likelihood of survival as defined by a Sepsis-related Organ Failure Assessment score (SOFA score) of > 11 points ²

- b. Immunocompromised patients (HIV with CD4 <200 cells/mm³, corticosteroids > 0.5 mg/kg per day for > 30 days, received chemotherapy in the past 3 months, solid organ or hematopoietic cell transplant)
- c. Patients receiving antibiotic therapy for any other defined extra-pulmonary infections that warrant a duration of antibiotics longer than 7 days or complications of pneumonia such as lung abscess or empyema that warrant a duration of antibiotics longer than 7 days (excluding anti-tuberculosis treatment, antifungal medications, antibiotics meant for chronic suppression of chronic infections or chronic obstructive lung disease)
- d. Patients who have been treated for VAP for more than 7 days from screening
- e. Vulnerable population including prisoners and refugees

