In the short duration arm, all antibiotics should be withdrawn by day 7 (short duration) according to the randomisation assignment, except for those participants with treatment failure in the case of persistent VAP or a new-onset infection of a different source prior to the last day of assigned duration of antibiotics. Persistent VAP or treatment failure is defined as the lack of improvement of hemodynamic stability or ventilation requirements without an alternative cause other than the same episode of VAP. These patients will continue to be monitored for the above-described “fitness criteria” and antibiotics should be stopped when they eventually meet the criteria. Recurrent VAP is defined as an additional episode of VAP satisfying the CDC clinical and radiological criteria of VAP¹ following commencement of the primary VAP treatment within $60(\pm 5)$ days of enrolment. Opinion from 2 respiratory experts blinded to the randomisation will be sought to diagnose persistence and recurrences. Patients who are diagnosed with an alternative source of

infection or a complication from VAP such as lung abscess or empyema that warrant a duration of antibiotics longer than 7 days prior to the last day of assigned duration of antibiotics are not considered treatment failures. These patients will not meet fitness criteria for randomisation and be discontinued from the study and subsequent analysis. In cases where patients are randomised to short duration and satisfy the above-described “stop criteria” but did not have their antibiotics stopped by day 7, they are considered protocol deviations. They will be analysed in the intention to treat analysis according to arm they are randomised to.

Duration of antibiotics in the control group will be at least 8 days with the exact duration decided by the managing physicians.

Adverse events will be recorded throughout the study period, including *C. difficile* infection, acute kidney injury, hepatitis, drug allergies, haematological and other complications, readmissions.

Blinding

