2.6. Hypotheses and Definition of Primary and Secondary Outcomes

Primary end point

The primary end point of the study is the difference in the proportion of participants with the composite endpoint of death and VAP recurrence rate within 60(± 5) days of enrolment.

Death refers to all-cause mortality. VAP recurrences are episodes which satisfy the US CDC VAP criteria, and verified by two independent respiratory or infectious diseases physicians blinded to the randomisation arm.

The first statistical test for the primary end point will be for non-inferiority. Here, the null hypothesis (H_0): $\theta \geq \delta$ will be tested against the alternative (H_1): $\theta < \delta$, where θ is the treatment effect difference between the proportion of participants who have the primary outcome in the short and long treatment strategy groups, and δ is the fixed non-inferiority margin of 12%.

In the event that short is non-inferior to the long treatment strategy, standard two-sided superiority testing will be performed. That is, the null hypothesis (H_0): $\theta = 0$ will be tested against the alternative (H_1): $\theta > 0$, where θ is the treatment effect difference between the proportion of participants who have the primary outcome in the short and long treatment strategy groups.

Secondary end points

All statistical tests for the secondary endpoints are standard two-sided superiority tests.

a) Ventilator-associated events

Definition: Events which satisfy the US CDC VAP criteria ¹ but were not verified by two independent respiratory or infectious diseases physicians.

H_0 : There is no difference in the proportion of participants who have ventilator-associated events in the short and long treatment strategy groups, i.e. $\theta^{VAE} = 0$;

H_1 : There is a difference in the proportion of participants who have ventilator-associated events in the short and long treatment strategy groups, i.e. $\theta^{VAE} \neq 0$;

where θ^{VAE} is the treatment effect difference between the proportion of participants in the short and long treatment strategy groups.

b) Duration of mechanical ventilation

Definition: Total duration of mechanical ventilation during the 60 days of follow-up after enrolment.

H_0 : There is no difference in the total duration of mechanical ventilation in the short and long treatment strategy groups, i.e. $t^v_s = t^v_l$;

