2.7. Outcomes Assessment Schedule

Baseline assessments are performed prior to randomisation on day 0. Other important assessment time points are detailed below.

Time point (Day)	Activity
0	Enrolment, baseline assessments.
Antibiotic prescription	
0-7	Antibiotic choice(s) is / are checked against respiratory endotracheal tube cultures. If current antibiotic choice(s) is / are not appropriate, primary physicians are advised to switch antibiotic choice according

	
to antibiotic susceptibility report (when there is positive growth) or local microbiology antibiogram (when there is no positive growth).
 
Randomisation to short or long treatment strategy. If randomisation is to short arm, all antibiotics for the participant should be stopped on the day of randomisation (other than, when applicable, anti-tuberculosis antibiotics, prophylaxis e.g. peri or post operative or in immunocompromised hosts, gut prokinetic antibiotics)

0 - discharge	Weekly follow-up for new or changes in antibiotic prescription for all participants.
Outcome assessment	
0 - discharge	
New or changes in antibiotic prescription or new respiratory culture reports will trigger screening for pneumonia recurrence. The US CDC VAP diagnostic criteria will be checked during the preceding week.
 
When these diagnostic criteria are met, two independent respiratory or infectious diseases physicians who are blinded to the randomisation arm will be consulted to verify if the episode is a recurrent episode.

0 - 60	
Mortality is assessed weekly.
 
Secondary outcomes such as adverse events, discharge / readmissions, intubation / extubation, clinical cultures, biochemistry laboratory tests are recorded weekly.

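### The ventilator-associated event definition does not exclude the index pneumonia, so persistence that is re-screened, and findings from before randomisation, can be counted as events

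*SAP*

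**What the plan says.** - **Entry.** SAP 2.3 requires each participant to "Satisfy the US Centers for Disease Control and Prevention National Healthcare Safety Network VAP diagnostic criteria".
- **Event.** SAP 2.6(a) covers "Events which satisfy the US CDC VAP criteria", and then restricts this to those that "but were not verified by two independent respiratory or infectious diseases physicians". SAP 8.2 turns it into an ever/never variable per participant and adds no limit on onset.
- **Window.** SAP 2.1 introduces the secondary endpoints with "To compare the following endpoints according to treatment allocation within 60 days of enrolment". Randomisation comes later than enrolment: SAP 2.4 makes it conditional on the fitness criteria, and SAP 2.7 places it within days 0 to 7.
- **Detection.** SAP 2.7 runs outcome screening from day 0 to discharge. A new or altered antibiotic order, or a fresh respiratory culture result, sets off a screen, and "The US CDC VAP diagnostic criteria will be checked during the preceding week". Episodes that pass go to two blinded physicians, whose question is whether the episode is a recurrence.
- **Persistence.** SAP 2.4 adds that "Opinion from 2 respiratory experts blinded to the randomisation will be sought to diagnose persistence and recurrences". No section says whether an episode classed as persistence counts as a ventilator-associated event.

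**The concern.** The event is a residual category: it meets the criteria but is not a verified recurrence. A residual category is only as clean as the rule that keeps other things out of it, and here nothing keeps out the pneumonia that brought the participant into the trial. Two kinds of non-outcome can enter: findings that pre-date randomisation, which allocation cannot have caused, and continuation of the index VAP.

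The SAP has suitable limits for other outcomes. SAP 2.4 requires a recurrence to be a further episode, and SAP 8.8 restricts bloodstream infections to those after randomisation. SAP 2.6(a) and 8.2 do neither.

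At stake is how this one secondary comparison can be read. Equal carry-over in the two arms pulls the difference towards zero; unequal carry-over produces a difference that is not a treatment effect. If the rule stays unwritten, it will be chosen at analysis by a statistician who, under SAP 9.2, knows the allocations.

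**Working it through.** The plan states no event rate or power for this endpoint, so there is no figure to reproduce. The check is a walk through the text, followed by an illustration.

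**Step 1: the route through the text**

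1. A participant is enrolled on day 0. Protocol 7.2 allows up to 72 hours between fulfilling the criteria and recruitment, so the criteria were met between day −3 and day 0.
2. Protocol 5 calls for a respiratory sample within 24 hours of enrolment if none has been taken. Protocol 7.7 says "Culture results with antibiogram are usually available within 48 to 72 hours after sample collection". For a sample taken on day 0 or 1, the report arrives between day 0 + 2 = 2 and day 1 + 3 = 4.
3. If that report triggers a screen, the look-back starts between day 2 − 7 = −5 and day 4 − 7 = −3, so it covers the date on which the entry criteria were met. More generally, any trigger up to day 7 reaches back to day 0. An antibiotic switch, which SAP 2.7 foresees in days 0 to 7, is also a trigger as worded.
4. The screen is positive on the index findings. The two physicians are asked whether this is a recurrence and correctly answer no.
5. The episode now meets the criteria and is not verified. That is the SAP 2.6(a) definition.

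Meeting the fitness criteria does not close this route. They cover temperature and haemodynamics only (SAP 2.4). The imaging, white-cell, secretion and gas-exchange items are not part of them, and a core temperature above 38.0 and up to 38.3 °C satisfies both the fitness limit and the entry temperature item.

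**Step 2: what equal carry-over does**

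Let p be the true proportion with a new event and s the proportion scored only because of the index episode, independent of p. Because the endpoint is ever/never:

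observed rate = s + (1 − s)p, so observed difference = (1 − s) × true difference.

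Inputs:
- n = 230 per arm (SAP 2.2).
- Two-sided 5% test (SAP 2.6 and 7.3).
- True rates of 20% and 30%. These are assumptions; the documents give none.
- s = 0, 0.20, 0.25 and 0.35. These are also assumptions.

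Power = Φ[(d − 1.96·SE0)/SE1], where d is the observed difference, SE0 = √(2·p̄(1 − p̄)/n) and SE1 = √((p1(1 − p1) + p2(1 − p2))/n).

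| s | Observed rates | d | Power |
|---|---|---|---|
| 0 | 20.0% v 30.0% | 10.0 points | 70% |
| 0.20 | 36.0% v 44.0% | 8.0 points | 42% |
| 0.25 | 40.0% v 47.5% | 7.5 points | 37% |
| 0.35 | 48.0% v 54.5% | 6.5 points | 29% |

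For s = 0.20: 0.20 + 0.80 × 0.20 = 0.36 and 0.20 + 0.80 × 0.30 = 0.44. SE0 = 0.0457 and SE1 = 0.0455, so (0.08 − 1.96 × 0.0457)/0.0455 = −0.21 and Φ = 0.42.

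**Step 3: unequal carry-over**

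With no true difference, the observed difference is (s_short − s_long)(1 − p), which is not zero unless carry-over is the same in both arms. One mechanism is visible in the text. SAP 2.7 has short-arm antibiotics stopped on the day of randomisation, within days 0 to 7. If a stop counts as a change in prescription, it triggers a screen while the index findings are still inside the look-back. Long-arm stops come later. SAP 2.7 does not say whether a stop counts.

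**The case against.** The best defence is that SAP 2.6 defines recurrence and ventilator-associated event in parallel. Both use the same criteria; one is verified and the other is not. SAP 2.7 screens for recurrence and refers every positive screen to blinded physicians, so an event is naturally read as a candidate recurrence that they did not confirm. The criteria also ask for new, progressive or worsening findings, so a stable or resolving infiltrate does not qualify again merely by persisting. SAP 2.7 deals with index cultures and antibiotic switches in its own antibiotic rows, which suggests they were not meant as outcome triggers. Finally, randomised participants have met the fitness criteria, so carry-over should be lower than in unselected VAP.

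Much of this stands, and it limits the point:

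- A reader might infer that the index pneumonia scores automatically for everyone. The documents do not support that: a trigger, a positive screen and a referral come first. Automatic scoring would put both arms at 100% and cannot be intended.
- It would be wrong to say that events go unreviewed. The physicians see each positive screen. The gap is that 'not verified' could mean rejected, discordant or never reviewed.
- It is tempting to take the Protocol's remark "despite persistence of signs and symptoms of pneumonia in 35% of these patients" as a carry-over rate. It comes from another study of culture-negative patients, has no time point, and does not measure whether the CDC criteria were met.

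It does not remove the gap. The new and worsening items do not help when the look-back itself contains the days on which the index findings were new. The outcome row in SAP 2.7 starts at day 0 and exempts neither index reports nor switches. The natural reading of an event as an unconfirmed candidate recurrence still takes in an index episode that was correctly refused as a recurrence.

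**Conclusion.** The concern holds in a limited form. Followed as written, SAP 2.6(a), 2.7 and 8.2 allow continuing index pneumonia and pre-randomisation findings to be counted as ventilator-associated events. This is more than a missing detail, because the residual rule assigns a correctly refused index episode to the event count.

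The size cannot be known from the documents. It depends on how often a first-week trigger leads to a positive screen on index findings. The fall in power from 70% to 42% rests on the assumed 20% and 30% rates and an assumed 20% carry-over, equal in both arms; it shows sensitivity and is not an estimate. Bias between arms is possible but conditional on how triggers are counted.

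A reader might infer that the non-inferiority conclusion is at risk. It is not: recurrence must be a further episode and must be verified, so the primary endpoint is unaffected. This is one secondary endpoint, and its definition should be corrected before analysis.

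**What to change.** Amend SAP 2.6(a), 2.7 and 8.2 so that:

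1. only episodes with onset after randomisation count as ventilator-associated events;
2. for this endpoint the look-back starts no earlier than randomisation;
3. episodes that the two experts class as persistence of the index VAP are excluded;
4. 'not verified' is defined, stating whether it means reviewed and rejected, and how discordant or unreviewed episodes are handled.

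Do not require separate proof that the index episode had resolved. The criteria are checked only when triggered, so that information may not exist, and the recurrence definition does not ask for it.

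The cost is wording, and fewer counted events. The persistence judgement is already planned in SAP 2.4. One practical limit is that the dates listed for full checking in SAP 3 do not name the dates of individual CDC findings, and recruitment has closed (SAP 2.2). The amendment should therefore also say in advance how onset is assigned when those dates are missing. No change to patient care is involved.
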